5.2 Demographic and Baseline-Related Definitions

Change (absolute change) from Baseline

The arithmetic difference between a post-randomization value and baseline for a given time point:

Change from baseline = (post-randomization value – baseline value)

Percent Change from Baseline

The percent change from baseline for a given variable at a given time point is defined as:

$100 \times \text{change from baseline} / \text{baseline value}$

Change (absolute change) from Parent EOS

The arithmetic difference between a post-enrollment value and the last lipid measurement used in the primary analysis of the parent study:

Change from parent EOS = (post-enrollment value – last observed lipid measurement used in parent primary analysis), where the last observed lipid measurement used in the parent primary analysis will be the week 6 value observed in study 20120348, the week 52 value observed in study 20110109, and the week 12 value observed in other studies. If the observation is missing, the subject will be excluded from change from parent EOS analysis of the particular analyte.

Percent Change from Parent EOS

The percent change from parent EOS for a given variable at a given time point is defined as:

$100 \times (\text{change from parent EOS}) / \text{last lipid measurement used in parent primary analysis}$

5.3 Other Study Related Definitions

Analytical Study Week Assignments

Analytical windows will be used to assign parameters to study weeks. The Algorithm is provided in [Appendix A](#).

IP Exposure Period in Months

IP Exposure = $[(\min(\text{EOIP date} + 28 \text{ days}, \text{EOS date}, \text{data cutoff date}) - \text{First dose date}) + 1] / 365.25 * 12$. For subjects randomized to SOC treatment during the SOC-Controlled period, the first dose date is equivalent to the first dose date during the All-IP period.

Study Exposure Period in Months

For each randomized subject, Study Exposure Period = $[\min(\text{EOS date}, \text{data cutoff date}) - \text{enrollment date}] + 1 / 365.25 * 12$

IP Exposure in Months During the SOC-Controlled period

For subjects randomized to AMG 145+SOC arm and received at least one dose of AMG 145 in the SOC-Controlled period, IP Exposure during the SOC-Controlled period = $[(\min(\text{EOIP date} + 28 \text{ days}, \text{end of SOC-Controlled period}) - \text{Study Day 1}) + 1] / 365.25 * 12$. Any IP exposure < 0 will be considered as N/A.

For subjects randomized to SOC or randomized to AMG 145 + SOC and not dosed in the SOC-Controlled period, IP Exposure during the SOC-Controlled period = N/A.

IP Exposure in Months During the All-IP period

For each randomized subject in the Interim All-IP period Analysis Set, IP Exposure during the All-IP period

= $[(\min(\text{EOIP} + 28 \text{ days}, \text{end of All-IP period}) - \text{start date of All-IP period}) + 1] / 365.25 * 12$. If the above calculation is < 0 , then set to 0.

Study Exposure in Months During the SOC-Controlled period

For each randomized subject, Study Exposure Period for the SOC-Controlled period = $[(\text{end of SOC-Controlled period date} - \text{start of the SOC-Controlled period}) + 1] / 365.25 * 12$.

Study Exposure in Months During the All-IP period

For each randomized subject that received a dose of IP during the All-IP period,

Study Exposure Period for the All-IP period = $[(\text{end of All-IP period} - \text{start of the All-IP period}) + 1] / 365.25 * 12$.

Adverse Events Included in the Summary Tables

An adverse event is included in SOC-Controlled period summaries if it occurs during the SOC-Controlled period and the subject is in the Interim SOC-Controlled period Analysis Set.

An adverse event is included in All-IP period summaries if it occurs during the All-IP period and the subject is in the Interim All-IP period Analysis Set.

Sex

For subjects that enroll in an extension study, the subject's sex is the sex recorded on the extension study eCRF. For other subjects, the subject's sex is the sex recorded on the parent study eCRF.

Race

For subjects that enroll in an extension study, the subject's race is the race recorded on the extension study eCRF. For other subjects, the subject's race is the race recorded on the parent study eCRF.

Country and Region

For subjects that enroll in an extension study, the subject's country and region are those recorded in the extension study. For other subjects, the subject's country and region are those recorded in the parent study.

Baseline Metabolic Syndrome

For each subject without type 2 diabetes mellitus, metabolic syndrome is identified by the presence of 3 or more of the components listed below (modified AHA/NHLBI criteria). Subjects with type 2 diabetes cannot be categorized as having metabolic syndrome.

Risk Factor	Defining Level
Elevated waist circumference:	
Non-Asian:	
Men	≥ 102 cm
Women	≥ 88 cm
Asian:	
Men	≥ 90 cm
Women	≥ 80 cm
Triglycerides	≥ 150 mg/dL
HDL cholesterol	
Men	< 40 mg/dL
Women	< 50 mg/dL
Blood pressure	SBP ≥ 130 mmHg or DBP ≥ 85 mmHg OR Hypertension checked 'yes' on CV Medical History eCRF
Fasting glucose	≥ 100 mg/dL

4-Level Treatment Group

All tables in this interim analysis will be summarized by randomized group (AMG 145+SOC vs. SOC alone). Since subjects received either AMG 145 or control treatment in parent study, the tables will be further categorized using the following 4 levels (parent study treatment group/current study treatment group): "AMG 145/AMG 145 + SOC"; "AMG 145/SOC Only"; "Control/AMG 145 + SOC", and "Control/SOC Only".

6. Analysis Subsets

Interim SOC-Controlled period Analysis Set

The Interim SOC-**C**ontrolled period **A**nalysis **S**et (ICOAS) will include all subjects randomized in this study who have at least 12 weeks of potential follow-up (eg. subjects for whom Data Cutoff Date - Study Date for Study Day 1 + 1 > 91 days); the restriction on potential follow-up is to prevent operational bias that may occur by the increased frequency of visits during the first 12 weeks of the study. Subjects will be analyzed according to the treatment group to which they were randomized during the SOC-Controlled period. All data from the SOC-Controlled period will be summarized, regardless of possible IP discontinuation.

Interim All-IP period Analysis Set

The Interim All-IP period Analysis Set (IAAS) will include all subjects that were randomized **in this study** and dosed with IP and on-study in the All-IP period. Data will be summarized analyzed from the start of the All-IP period to EOS or the data cutoff, whichever occurs first.

7. Data Screening and Acceptance

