10.1.5 Analysis Sets

The full analysis set (FAS) will include all subjects randomized in this study. All analyses of the randomized controlled period of the study will be performed using the FAS. Analyses of the period after the randomized controlled period may be limited to those receiving investigational product.

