IVRS	Interactive voice response system
LDL-C	Low density lipoprotein cholesterol
LFT	Liver Function Test
Lp(a)	Lipoprotein(a)
MedDRA	Medical dictionary for regulatory activities
OLE	Open label extension
QM	Every month
Q2W	Every 2 weeks
SOC	Standard of care
SAP	Statistical analysis plan
TIA	Transient ischemic attack
ULN	Upper limit of normal
VLDL-C	Very low density lipoprotein cholesterol

1. Introduction

The purpose of this interim SAP is to pre-specify interim analyses to support regulatory filings. The analysis strategy is consistent with the protocol specified analysis. Analyses will be performed based on datasets of an ongoing study 20120138, entitled A Multicenter, Controlled, Open-label (OLE) Study to Assess the Long-term Safety and Efficacy of AMG 145 (latest amendment 2 is 30 APR 2013).

2. Objectives

The objective for this analysis is to summarize the safety and lipid data collected up to a cutoff date reported in the table outputs for subjects rolled over from parent studies into the extension study 20120138. All data prior to the data cut date will be collected, checked and queried in the similar fashion as the final database lock.

3. Endpoints

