5.1 Study Time Points

Baseline

For variables other than sex, race, country, region, and baseline metabolic syndrome, baseline is defined as the parent study baseline. Note that baseline metabolic syndrome will be using parent study baseline information, but with updated sex and race from the extension study data.

First Dose Date

For subjects randomized to AMG 145+SOC, the first dose date is the first date at which the subject was administered IP. For subjects randomized to SOC, the first dose date is the first date at which the subject was administered IP at or after the Week 48 clinical visit.

End of Investigational Product (EOIP) Date

If a subject has completed or discontinued IP, the EOIP date is the date recorded on the final IP dose date eCRF.

End of Study (EOS) Date

For each subject, the End of Study Date is the date recorded on the End of Study eCRF.

Enrollment Date

The enrollment date for a subject is either the subject's EOS date for the parent study or the date that subject has signed the ICF for Study 20120138, whichever is later.

Randomization Date

The randomization date for each subject is the date the investigator (or designee) confirms in the IVRS that the subject has met all eligibility criteria and is randomized.

Study Day 1

For subjects randomized to AMG 145+SOC arm and received at least one dose of AMG 145, Study Day 1 is defined as the first day that AMG 145 is administered during this study.

For subjects randomized to SOC only arm, or randomized to AMG 145+SOC arm but never received AMG 145, Study Day 1 is defined as the day of randomization.

Study Day

For each subject, and for a given study visit date, study day is defined as the number of days since Study Day 1:

$$\text{Study day} = (\text{study visit date} - \text{Study Day 1 date}) + 1$$

If the date of interest is prior to the Study Day 1:

$$\text{Study day} = (\text{study visit date} - \text{Study Day 1 date})$$

SOC-Controlled period

The start of the SOC-Controlled period is Study Day 1.

For the end of the SOC-Controlled period:

- If a subject is administered a dose of IP at Week 48, the day prior to the week 48 IP date is the end of the SOC-Controlled period.
- If a subject is not administered a dose of IP at Week 48, the SOC-Controlled period will end the earliest of Study Day 343, the EOS date, or data cutoff date.

All-IP period

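### At an interim cutoff during or soon after enrolment, adverse events and serious adverse events in subjects at Study Day 91 or earlier enter no AE summary table

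*SAP*

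**What the plan says.** Protocol 10.1.5 defines one analysis set, "The full analysis set (FAS) will include all subjects randomized in this study", and adds that "All analyses of the randomized controlled period of the study will be performed using the FAS".

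The interim SAP uses a narrower set. Under SAP 6 the ICOAS "will include all subjects randomized in this study who have at least 12 weeks of potential follow-up", illustrated as "subjects for whom Data Cutoff Date - Study Date for Study Day 1 + 1 > 91 days". The reason given is that "the restriction on potential follow-up is to prevent operational bias that may occur by the increased frequency of visits during the first 12 weeks".

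SAP 5.3 ties event counting to set membership. A controlled-period AE is summarised if it "occurs during the SOC-Controlled period and the subject is in the Interim SOC-Controlled period Analysis Set". All-IP period AEs follow the same pattern with the IAAS. SAP 8.1 makes these two sets the default for every analysis unless something else is specified, and 8.4.1 repeats this for AEs.

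SAP 1 says that "The analysis strategy is consistent with the protocol specified analysis". SAP 2 gives the objective as summarising safety and lipid data up to the cutoff for subjects who rolled over.

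**The concern.** The interim analyses are meant to support regulatory filings. A subject who started shortly before the cutoff has data that are collected, checked and queried, yet the AE rule leaves that subject's events out of the AE and SAE tables. The subjects concerned include those who had control in the parent study and are in their first weeks on AMG 145.

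The stated reason is visit frequency. That is a fair concern for routine AEs, because early contact differs by arm: training visits on site for AMG 145 subjects new to self-injection, phone visits for SOC-alone subjects. It carries much less weight for serious events. Protocol 9.2.2 requires SAEs to be submitted within 24 hours of the investigator's knowledge, and deaths and major cardiovascular events are independently adjudicated. The SAP nevertheless applies one exclusion to all of them and plans no supplementary all-randomised safety table.

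**Working it through.** **1. Where the cut falls.** Let C be the cutoff and D be Study Day 1. A subject is included if C − D + 1 > 91, that is, C − D ≥ 91. Gaps of 0 to 90 days are excluded, which is 91 calendar days. Twelve weeks is 84 days, so the inequality is 7 days longer than the words beside it. The scheduled Week 12 day under SAP Appendix A is 7 × 12 + 1 = 85, and adding the protocol's 7-day visit window gives 92, the first included study day. That may be the intent, but the SAP does not say so.

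**2. Whose clock.** For dosed AMG 145 + SOC subjects, "Study Day 1 is defined as the first day that AMG 145 is administered during this study" (SAP 5.1). For SOC-alone and never-dosed subjects it is the day of randomisation.

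**3. Tracing an excluded subject through the SAP.**
- At the cutoff the subject is at Study Day 91 or earlier, well short of Week 48 and of Day 343.
- Under SAP 5.1 the SOC-Controlled period therefore ends at EOS or the cutoff, and the All-IP dates are missing.
- The IAAS requires dosing in the All-IP period, so the subject is in neither set.
- Under 5.3, no AE or SAE of this subject enters an AE summary. SAP 7.3.3 starts from including all AEs but excepts those outside the 5.3 definitions, so it leads back to the same rule.

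**4. What is not settled.** SAP 8.2 tabulates IP and study discontinuation with reasons, by period and overall, and names no set. Protocol 8.1 lists adverse event as a reason for stopping IP and death as a reason for leaving the study. SAP 8.4.3 summarises adjudicated events, including all-cause death, by period and also names no set. Whether the 8.1 default governs these two sections cannot be decided from the text.

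**5. The protocol's own precision figure.** Expected N = 3478 + 950 = 4428, split 2:1 into 2952 and 1476. At 5% incidence that is 148 and 74 events. Exact (Clopper-Pearson) 95% intervals are 4.25% to 5.86% and 3.96% to 6.25%, which match the stated (4.3%, 5.9%) and (4.0%, 6.3%). Those figures use everyone randomised. If 25% were excluded (n = 2214 and 1107), they would widen to 4.1% to 6.0% and 3.8% to 6.4%, a small loss of precision.

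**6. How many could be affected.** The documents give neither accrual dates nor a cutoff date. As an illustration only, assume uniform accrual over A days running up to the cutoff, with N = 3478 (the number enrolled in protocol 10.2; the number at an actual interim cutoff is not given). Then:
- share excluded = 91/A
- excluded patient-years = N × (1 + 2 + … + 91) / (A × 365.25) = N × 4186 / (A × 365.25)
- the last column caps each subject's controlled follow-up at 343 days.

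| A (days) | Share excluded | Subjects | Patient-years | Share of controlled person-time |
|---|---|---|---|---|
| 182 | 50% | 1739 | 219 | 25% |
| 365 | 25% | 867 | 109 | 6% |
| 548 | 17% | 578 | 73 | 3% |
| 730 | 12.5% | 434 | 55 | 2% |
| every Study Day 1 at least 91 days before cutoff | 0 | 0 | 0 | 0 |

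The documents give no SAE rate, so no count of missing SAEs is offered.

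**The case against.** The restriction is disclosed and reasoned. It depends on potential follow-up, so someone who died or withdrew early stays in if Study Day 1 is early enough. It applies to both arms by calendar time. This is an interim SAP: the protocol FAS still stands for the study, and excluded subjects enter at later cutoffs. SAEs reach the sponsor and regulators by expedited reporting whatever these tables contain. All of this stands, and it limits the harm to completeness.

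Protocol 10.3 places the controlled-period interims after sets of parent studies have finished Week 48, when no subject in those sets would be dropped. That also stands, but 10.3 does not confine interims to that timing, and a rule on 12 weeks of potential follow-up has an effect only at a cutoff taken during or soon after enrolment.

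The SAP cites protocol Amendment 2, while the protocol available is Amendment 6. The Amendment 2 wording of the FAS cannot be checked, so the SAP's statement of consistency cannot be shown to have been wrong when written. The conflict with the current protocol and with the SAP's own objective remains.

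A reader might infer that deaths and serious events in these subjects appear in no planned table at all. The documents do not support that: the discontinuation summary in 8.2 and the adjudicated-event summary in 8.4.3 may capture deaths, AE-driven IP withdrawals and adjudicated events.

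**Conclusion.** The point holds for the AE tables. At an interim cutoff within 91 days of some subjects' Study Day 1, their AEs, SAEs and AEs leading to IP withdrawal are counted in no AE summary. That follows from SAP 5.1, 5.3 and 6 without any assumption. For deaths and adjudicated events the finding is only that the governing set is unclear.

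The size is unknown. It runs from zero to, under uniform accrual up to the cutoff, the shares in the table. Actual accrual followed parent-study completion and is unlikely to have been uniform.

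A reader might also infer that the safety comparison between arms is biased. The documents do not support a material bias: the cut is by date, not outcome, and applies to both arms. The different Day 1 definitions should matter little, since protocol Appendix A schedules randomisation and first dose for the same visit. What is lost is completeness of interim safety reporting and a little precision. If the overall exposure summary in SAP 8.4.7 covers everyone randomised, it would also include person-time whose AEs are not counted.

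**What to change.** - Keep the ICOAS for routine AE incidence.
- In SAP 8.4.1 and 8.4.3, add tables of deaths, SAEs, AEs leading to IP withdrawal and adjudicated events by randomised arm for all randomised subjects. Limit them to the SOC-Controlled period as defined in SAP 5.1, ending at the cutoff if that is earlier. Running them by randomised arm to the cutoff for everyone would credit on-drug events after Week 48 to the SOC-alone arm.
- Name the analysis set for 8.2 and 8.4.3.
- State in SAP 1 and 6 that the ICOAS differs from the protocol FAS, and why.
- Reconcile the 12-week wording with the 91-day inequality in SAP 6.

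The cost is SAP wording and a few repeat tables on data already collected and queried. The downside is a second denominator, which needs a footnote.

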7.1 General Principles

The objective of the data screening is to assess the quantity, quality and statistical characteristics of the data relative to the requirements of the planned analyses.

7.2 Data Handling and Electronic Transfer of Data

Amgen's Clinical Data Management department will provide all data to be used in the planned analyses. This study will use the RAVE database.

All data collected in the eCRF will be extracted from RAVE. Protocol deviations will be transferred from eClinical. Details on data transfer will be provided in the Data Transfer Plan.

7.3 Handling of Missing and Incomplete Data

7.3.1 Patterns of Missing Data

Subjects may be missing specific data points for various reasons. In general, data may be missing due to a subject's early withdrawal from study, a missed visit, or non-evaluability of a data point or an endpoint at a particular point in time. All attempts will be made to capture missing or partial data for this trial prior to the data cutoff date.

The frequency and pattern of missing data for selected endpoints will be assessed through descriptive summaries of the measurements over time.

7.3.2 Missing Lipid Panel Endpoint

There will be no imputation for missing lipid panel endpoints.

7.3.3 Handling of Incomplete Dates

All adverse events will be included in adverse events summaries with the following exceptions: adverse events with complete dates occurring outside the definitions established in [Section 5.3](#) and adverse events with partially missing dates for which there is sufficient information to determine the event occurred outside these definitions. For partially missing dates or completely missing dates for which it is impossible to determine whether the event occurred outside these definitions, the event will be treated as occurring during the SOC-Controlled period.

Concomitant medication with partially missing dates will be imputed as described below:

- If year is available but day and month are missing, the day and month for the start date will be set to the 1st of January of the onset year.
- If year and month are available but day is missing, the day will be set to the 1st of the month of the onset year.

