Study Design: This is a multicenter, randomized, controlled, open-label extension study designed to assess the long-term safety and efficacy of AMG 145. Subjects that successfully complete a qualifying protocol and sign informed consent will be randomized 2:1 to one of two groups: AMG 145 + standard of care (SOC) or SOC-alone. Subjects randomized to the treatment group will also be expected to take background lipid lowering therapy and will be able to choose from one of two dose regimens: AMG 145 (140mg) administered every 2 weeks (Q2W) + SOC, or AMG 145 (420mg) administered monthly (QM) + SOC. Subjects randomized to the control group will receive SOC alone for the first 48 weeks of the study. During the first 12 weeks of the study participation, LDL-C will remain blinded and subjects must remain on stable background lipid lowering therapy. Using clinical judgment, the primary investigator or qualified delegate should recommend background lipid lowering therapy the subject can be expected to tolerate: therapy either prescribed to them PRIOR to participation in parent study, or statin or ezetimibe therapy given during parent study. Investigators will be informed if triglycerides are > 1000 mg/dL (11.3 mmol/L) so that appropriate subject follow-up can be initiated if necessary (see Protocol [Section 6.1.3.4](#)). Randomization should occur within 30 days after the parent study's EOS visit. Subjects will be stratified by their parent study and frequency of SC dose (Q2W or QM) within the parent study. After Week 48 all subjects will receive open-label AMG 145 for up to 2 years (or until the investigator's recommendation for discontinuation, Amgen's recommendation for discontinuation, the subject's decision to discontinue for any reason, or until an administrative decision is made to close the study).

Sample Size: The number of subjects entering this study will depend on the number of subjects completing their respective AMG 145 parent studies and willingness to enroll. Approximately 4428 subjects are expected to participate in this study.

Summary of Subject Eligibility Criteria: Subjects who complete a qualifying AMG 145 protocol and do not discontinue IP in the parent study for any reason including an adverse event will be eligible for this study. For a full list of eligibility criteria, please refer to [Section 4.1](#) and [Section 4.2](#).

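### Adverse events that cannot be dated are all placed in the SOC-Controlled period, so possible on-drug events in SOC-alone subjects who have started AMG 145 count as untreated and drop out of the All-IP summaries

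*SAP*

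**What the plan says.** SAP Section 7.3.3 first leaves out of a period's summaries any event whose complete date falls outside the Section 5.3 definitions, and likewise "adverse events with partially missing dates for which there is sufficient information to determine the event occurred outside these definitions". Where a partial or absent date leaves the period unsettled, "the event will be treated as occurring during the SOC-Controlled period". The rule does not depend on randomized group or on whether the subject has started AMG 145.

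These provisions decide where such an event is counted:

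- **Period boundary (SAP Section 5.1).** For a subject dosed at Week 48, "the day prior to the week 48 IP date is the end of the SOC-Controlled period". A SOC-alone subject's first dose date is defined as at or after the Week 48 visit.
- **Crossover (Protocol Synopsis, Study Design).** "After Week 48 all subjects will receive open-label AMG 145 for up to 2 years".
- **Grouping (SAP Section 6).** "Subjects will be analyzed according to the treatment group to which they were randomized during the SOC-Controlled period".
- **Summaries (SAP Section 5.3).** "An adverse event is included in SOC-Controlled period summaries if it occurs during the SOC-Controlled period", and "An adverse event is included in All-IP period summaries if it occurs during the All-IP period". Each also requires membership of the matching analysis set.
- **Endpoint (SAP Sections 3.1 and 8.4.1).** The primary endpoint is subject incidence of adverse events, tabulated separately for the two analysis sets. Injection-site reactions and hypersensitivity are among the listed categories.

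**The concern.** The same default means different things in the two groups. In AMG 145 + SOC the subject is assigned drug in both periods, so a wrong period does not change the treatment to which the event is attached. In SOC alone the controlled period is free of study drug (some of these subjects had AMG 145 in the parent study, but none receives it in this study before Week 48). There the default can turn an event that began after the first dose into an event under untreated control.

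An example is an injection-site reaction recorded with month and year only, in the month of the Week 48 dose. It would appear under SOC alone, in a period when that group receives no study injections, and would be missing from the All-IP table. At stake are the All-IP incidence, which describes exposure after the switch, and the credibility of SOC-alone counts in categories that should be close to empty.

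**Working it through.** **1. The plan's own figure.** Protocol Section 10.2 gives 4428 subjects (3478 + 950) and a 5% incidence for a particular adverse event. The 2:1 ratio gives 4428/3 = 1476 SOC alone and 2952 AMG 145 + SOC. Clopper-Pearson 95% intervals:

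- SOC alone, 74/1476: 3.96% to 6.25% (stated: 4.0% to 6.3%)
- AMG 145 + SOC, 148/2952: 4.25% to 5.86% (stated: 4.3% to 5.9%)

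Both agree within rounding. The SOC-alone half-width is (6.25 − 3.96)/2, about 1.15 points. The date rule itself has no stated figure.

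**2. Tracing one event.** Take a SOC-alone subject first dosed at Week 48, with a true onset after that dose and a date that cannot settle the period. Section 7.3.3 puts the event in the SOC-Controlled period. Section 6 counts it under SOC alone. Section 5.3 then keeps it out of All-IP. For an AMG 145 + SOC subject the same steps put the event in that group's controlled-period column.

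**3. Size, on assumptions.** The share of undatable events, *u*, is not in the documents; I take 0.5% to 5%. I also assume *p* = 5% in each period and group, independence between periods, every subject reaching All-IP, and one event per affected subject.

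- Events moved: n × p × u
- Recorded controlled-period rate: p + u·p·(1 − p)
- Recorded All-IP rate: p·(1 − u)

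| u | moved, SOC alone | moved, AMG 145 + SOC | controlled rate, each group | All-IP rate |
|---|---|---|---|---|
| 0.5% | 0.4 | 0.7 | 5.02% | 4.975% |
| 1% | 0.7 | 1.5 | 5.05% | 4.95% |
| 2% | 1.5 | 3.0 | 5.10% | 4.90% |
| 5% | 3.7 | 7.4 | 5.24% | 4.75% |

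The rise in SOC alone is 0.02 to 0.24 points. It reaches 0.25 (3.7/1476) if no affected subject already had the event in the controlled period.

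**4. Effect on the randomized comparison.** Let the true controlled-period rates be 5% on AMG 145 + SOC and 4% on SOC alone (ratio 1.25), with 5% in All-IP and the same *u* in both groups. At u = 5%:

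- SOC alone: 4% + 0.05 × 5% × 0.96 = 4.24%
- AMG 145 + SOC: 5% + 0.05 × 5% × 0.95 = 5.24%

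The difference is 0.998 points and the ratio 1.235. At u = 0.5% the difference is 1.000 and the ratio 1.248.

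**5. Near-empty categories.** One misplaced injection-site reaction adds 1/1476 = 0.07 points to SOC alone, and two add 0.14. These are small amounts, but plainly visible where the expected count is close to zero.

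**The case against.** A reader might infer that the rule resolves doubt in favour of the drug in the randomized comparison. The documents do not support that. The rule covers both groups, and at 2:1 allocation the AMG 145 + SOC column gains about twice as many events on twice the denominator. With equal undatable shares the difference hardly moves (step 4). A net bias would need undatable events to be more frequent among switched SOC-alone subjects, and nothing in the documents shows that. Equality is not assured either, since Week 48 is a first dose in this study only for SOC alone.

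A larger effect is also tempting. Ten such events would add 10/1476 = 0.68 points, but that would mean about 10/74 = 13.5% of the cases of a 5% event being undatable, each in a separate subject without that event in the controlled period. The documents offer no basis for such a share.

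There are also safeguards. Onset date is a required attribute (Protocol Section 9.1.2). The Week 48 injection is observed (Section 7.1.1.14) and followed by at least 30 minutes on site (Section 6.1.1). Subjects new to self-injection return within weeks for visits that include adverse event review (Sections 7.1.1.15 to 7.1.1.17). Data are queried as for a final lock (SAP Section 2), and missing data are pursued (SAP Section 7.3.1). First-dose reactions are therefore among the events most likely to be dated.

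All of this stands, and it limits the size. It does not correct the rule for the events that remain undatable. SAP Section 7.4 mentions sensitivity analyses only in general terms, and no count of rule-assigned events is planned.

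**Conclusion.** The point holds as a minor one. The rule can record a possible on-drug event in a switched SOC-alone subject as untreated and remove it from All-IP. All-IP incidence falls only where the subject has no other datable All-IP event in the same category, because the endpoint counts subjects. No bias in the randomized difference is established.

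On the assumptions in step 3 the size is 0.4 to 3.7 SOC-alone events, or 0.02 to 0.25 points on a 5% rate, against a half-width of about 1.15. Two things could lower it further at a given share. Only subjects who have entered All-IP by the cutoff can contribute, and that number is not given. The 1476 also comes from the current protocol total, whereas this interim SAP cites protocol Amendment 2. The undatable share is the assumption that matters most, and only the trial data can supply it.

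**What to change.** Amend SAP Section 7.3.3 in four parts:

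1. For any subject dosed in the All-IP period, in either group, include in the All-IP summaries as well every event whose date information cannot exclude onset on or after the start of that period.
2. Keep the current rule, applied alike to both groups, for the randomized SOC-Controlled comparison.
3. Add a sensitivity table that removes rule-assigned events from the controlled period in both groups.
4. Report the number of rule-assigned events by group.

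The controlled-period rule should not be changed for SOC alone only. With equal shares at u = 5%, both groups carry about 0.25 extra points (3.7/1476 and 7.4/2952). Removing them from one group would create a spurious gap of that size in the only controlled comparison.

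The cost is a few SAP sentences, a programming condition and one table. The All-IP rate will be slightly higher, since some events that truly began earlier will be counted there. Some events will appear in both period tables, so the two cannot be added, and a footnote should say so.
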